8. During the treatment period, fibrinogen should be measured daily. The aPTT should be measured at least daily, but preferably more often. The aPTT (for all patients on unfractionated heparin [UFH]) or anti-Xa (for all patients on low-molecular weight heparin [LMWH]) should be used to check the intensity of anticoagulation. In patients with moderate (creatinine clearance 30-50 ml/min) and mild (creatinine clearance 50-80 ml/min) renal impairment, careful clinical monitoring of anticoagulation intensity according to institutional guidance is advised. (more details see [Section 4.2.1](#))
9. PaO₂/FiO₂ is only measured during hospital stay. The qualifying PaO₂/FiO₂ ratio should be the worst measurement in the screening period. During the treatment period the worst measurement on a given day should be documented in the case report form. During the first 6 days and during the stay on ICU (whatever is longer), PaO₂/FiO₂ ratio should be measured at least three times daily in all patients, together with a recording of the patient's position.
10. The SOFA score will be assessed at baseline, Day 6 and Day 28 (or just before hospital discharge whichever comes first including vital signs assessment and laboratory samples needed for score calculations. (Please refer to [Appendix 10.1](#)). If patient is discharged from hospital prematurely, last evaluation during hospital stay is expected at day of discharge from hospital.
11. WHO clinical progression scale should be collected daily during hospital stay. The last measurement on a given day should be recorded in the case report form. On Day 1 (randomisation day) an assessment just before randomisation shall be collected as a baseline value.
12. Only applicable for women of childbearing potential. Urine pregnancy test will be performed at screening and at Visit 5. Study drug should only be administered in case of a negative test result. A woman is considered of childbearing potential, i.e. fertile, following menarche and until becoming post-menopausal unless permanently sterile. Permanent sterilisation methods include hysterectomy, bilateral salpingectomy and bilateral oophorectomy. Tubal ligation is NOT a method of permanent sterilisation. A postmenopausal state is defined as no menses for 12 months without an alternative medical cause.

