5.1.2 Oxygen- free and Ventilator-free days, days in ICU

Oxygen-free and ventilator-free days until Day 28 will be captured from source documents. Time-points of intubation and extubation will be recorded in the eCRF. Days on ICU, intermediate care, step-down unit (normal ward) will be counted until Day 28 based on source documents. Date of discharge from hospital and/or death will be recorded in the eCRF.

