6.2.2 Treatment periods

Randomisation of patients (Day 1, Visit 2a) shall happen not later than 24 hours after the confirmation of the inclusion and exclusion criteria. Study drug dispensing and administration shall start within 6 hours of randomisation. The time-point of obtaining D-Dimer levels can be as long as four calendar days before screening.

Treatment period duration is 5 days.

Interruptions for urgent reasons for a total of up to 72 hours are allowed and accordingly, the time window of the visits may be extended.

Patients who discontinue trial treatment prematurely should still follow the trial schedule until Visit 6/EOS, if possible, please see [Section 3.3.4](#), including vital status collection.

For the schedule of assessments and procedures during the treatment period refer to the [Flow Chart](#).

Please refer to [Table 4.1.4:1](#) for Dosing and Treatment schedule and Instructions for Dose calculation and Infusion rates of Alteplase ([Appendix 10.5](#))

For details on PK sampling collection please refer to [Section 5.3.1](#).

During the treatment period the worst measurement on a given day should be documented in the case report form. During the first 6 days and during the stay on ICU (whatever is longer), PaO₂/FiO₂ ratio should be measured at least three times daily in all patients, together with a recording of the patient's position.

Assessment of time-point of intubation and extubation, or start and end of non-invasive ventilation and oxygen support is collected.

In addition to the scheduled ECGs, ECGs should be done and documented at any time of clinical event (e.g. acute event of arrhythmia, tachy- or bradycardia, angina, or MI).

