- If day 6 value is missing, no Day 5 value available, but day 7 available, then day 7 value will be used
- Otherwise value set to missing for that patient.

Based upon this, the change from baseline for each patient will be calculated and used for the analysis.

Number of oxygen-free days (OFD) up to day 28, FAS, continuous endpoint

For this endpoint, 'oxygen-free' is defined as free from assistance from oxygen support. The number of oxygen-free days starts from when the patient has a 'lasting' value on the WHO clinical progression scale of ≤ 4 and ends on Day 28. A lasting value of ≤ 4 means that the value cannot exceed 4 at a later timepoint. If the patient is liberated from oxygen on Day x, then the number of OFDs is 28-x. If a patient has withdrawn consent prior to day 28 then he will have a missing value for OFD. In any case, if the status of the patient at Day 28 is death, as determined from the vital status page then the OFD=0.

Length of hospital stay up to day 28, FAS, continuous endpoint

This will be determined based upon the first hospital discharge date, or discharge to another care facility. If the patient dies within the first 28 day period, then length of hospital stay is 28.

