6.6 HANDLING OF MISSING DATA AND OUTLIERS

All efforts will be made to avoid having missing data in the database, however it is inevitable that there will be missing data, by design:

- For patients that die, there will be no further data, however this irreversible unfavourable state will be taken into consideration in the determination of each of the endpoints.
- For patients that are discharged from hospital before day 28, the only additional efficacy assessment is the vital status at days 28 and 90. The fact that the patient has improved in order to be discharged from hospital prior to day 28 will be taken into account in the determination of each of the endpoints.

Handling of missing data for the endpoints are outlined in [Section 5](#), in line with the definitions of the endpoints.

Missing or incomplete adverse event (AE) dates will be computed using the BI handling rules ([7](#)).

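### Oxygen-free days: the WHO-score rule in SAP (Part 2) 5.2.2 can miscount patients discharged on oxygen, and it bypasses the oxygen dates the protocol provides for

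*SAP*

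**What the plan says.** SAP (Part 2) 5.2.2 treats oxygen-free as having no oxygen assistance, with no restriction to the hospital stay. The count is tied to the WHO Clinical Progression Scale: "The number of oxygen-free days starts from when the patient has a 'lasting' value on the WHO clinical progression scale" of 4 or less. On what counts as lasting, it says "A lasting value of ≤ 4 means that the value cannot exceed 4 at a later timepoint". The formula is "If the patient is liberated from oxygen on Day x, then the number of OFDs is 28-x". Two exceptions are written: withdrawal of consent gives a missing value, and death by Day 28 gives 0.

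The protocol describes a different source. Section 5.1.2: "Oxygen-free and ventilator-free days until Day 28 will be captured from source documents". Section 6.2.2, on the treatment period, adds that "start and end of non-invasive ventilation and oxygen support is collected".

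On when scores exist, flow chart footnote 11 says "WHO clinical progression scale should be collected daily during hospital stay". SAP 6.6 says that for patients discharged before Day 28 "the only additional efficacy assessment is the vital status at days 28 and 90". However, the flow chart also marks the WHO scale at Day 28, and protocol section 6 has discharged patients invited to the remaining visits.

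**The concern.** The SAP's definition and its derivation agree only in hospital. In protocol Table 5.1.1:1, score 4 is hospitalised without oxygen, 5 is mask or nasal prongs, and 6 is NIV or high flow. Scores 0 to 3 grade viral RNA, symptoms and independence, and say nothing about oxygen. A patient who leaves hospital on oxygen moves to a part of the scale where oxygen cannot be seen.

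Number of oxygen-free days is a named Part 2 secondary efficacy endpoint. SAP 7.5.2 reports it from an ANCOVA with a treatment difference, confidence interval and p-value. That section also expects no missing values, so the gap would not show up as missing data. The trial is open-label, so discharge decisions are made with the arm known. If discharge on oxygen were more common in one arm, part of the estimated difference would reflect discharge practice rather than time off oxygen.

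**Working it through.** The documents give no planning figure for oxygen-free days, so there is nothing to reproduce. The check applies the SAP rule to patients discharged on oxygen and compares the result with the SAP's own definition.

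**Inputs.** Formula 28 − x, with x the first day of a lasting score of 4 or less (SAP 5.2.2). Meaning of the scores (protocol Table 5.1.1:1). The discharge and weaning days below are illustrations, not document figures.

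**Per patient**

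| Discharged on oxygen | Score recorded | Oxygen ends | SAP count | Count by definition | Error |
|---|---|---|---|---|---|
| Day 12 | 0–3 at discharge | still on at Day 28 | 28 − 12 = 16 | 0 | +16 |
| Day 20 | 0–3 at discharge | still on at Day 28 | 28 − 20 = 8 | 0 | +8 |
| Day 10 | 0–3 at discharge | Day 20 | 28 − 10 = 18 | 28 − 20 = 8 | +10 |
| Day 10 | last score 5 | Day 20 | 0 | 28 − 20 = 8 | −8 |
| Day 10 | last score 5 | still on at Day 28 | 0 | 0 | 0 |

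In the last two rows the 0 is inferred: with no qualifying score no day x exists, and the SAP states no default. A single ambulatory score at the Day 28 visit would give x = 28 and 28 − 28 = 0, the same result.

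Rows 3 and 4 are the same patient. The count is 18 or 0 depending on whether a score is entered at discharge, and the value by definition is 8.

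**Between arms.** Shift = (difference in share discharged on oxygen) × (error per affected patient). It is largest when every affected patient is scored 0–3 and stays on oxygen to Day 28. The shares are assumptions.

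- Day 12 discharge: 0.05 × 16 = 0.8 days; 0.10 × 16 = 1.6 days.
- Day 20 discharge: 0.05 × 8 = 0.4 days; 0.10 × 8 = 0.8 days.

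**Consistency with the protocol.** The Part 2 SAP (26 October 2021) is written to protocol Version 3. Global Amendment 2 (1 October 2021) had already added oxygen-free days to section 5.1.2 and oxygen-support collection to section 6.2.2, giving secondary-endpoint assessment as the reason for the latter. The SAP rule uses neither, and SAP section 4 does not list this among its changes.

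**The case against.** The strongest reply has four parts.

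First, scoring does not wholly stop at discharge. Footnote 11 limits only the daily collection, and a Day 28 score is scheduled for patients invited back. This stands, and a reader who takes SAP 6.6 alone might wrongly infer that no later score can exist. It does not rescue the rule, because an ambulatory score at Day 28 does not show whether the patient was on oxygen at home or when it stopped.

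Second, SAP 6.6 says that improvement sufficient for discharge will be reflected in each endpoint, and the primary endpoint counts discharge as success. That is a declared convention, but no rule for oxygen-free days follows from it, and 5.2.2 writes none.

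Third, the data largely exist. The protocol plans to capture oxygen-free days from source documents and to collect oxygen dates. This also stands. The defect is an unreconciled derivation rule, not an endpoint that cannot be measured.

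Fourth, the upper end of the range is generous. Protocol 7.5 assumes improvement or discharge in about 30% (SOC) and 50% (alteplase), a difference of 20 points, with an alteplase median of 20 to 30 days. A 10-point gap in discharge on oxygen alone would be half of that difference, and many discharges would fall later than Day 12. That is a fair reason to read 1.6 days as one end of a range. The exclusion of chronic lung disease requiring home oxygen removes some prior users, but not patients who newly need oxygen after COVID-19 ARDS.

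**Conclusion.** The concern holds in a limited form. The SAP rule can give a wrong oxygen-free-day count for a patient discharged on oxygen. It over-counts by up to 28 − x days (x the discharge day) if the patient is scored 0–3 at or after discharge. It under-counts if the last in-hospital score is 5 and oxygen stops at home before Day 28. The rule also departs from protocol 5.1.2 and 6.2.2 without saying so.

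Three stronger readings are not supported:

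- That every such patient is miscounted. With a last score of 5 and oxygen through Day 28, a count of 0 is correct.
- That the error favours a particular arm. The documents give neither the share discharged on oxygen nor any difference between arms, and the error can go either way. The 0.4 to 1.6 days rests on assumed differences of 5 to 10 points, discharge between Day 12 and Day 20, ambulatory scoring of all affected patients, and oxygen through Day 28.
- That the trial's main conclusions are at risk. Protocol 7.2.3 makes the analysis of the continuous endpoints non-confirmatory, and the endpoint lies outside the hierarchy in protocol 7.1. Alpha and the powered tests are unaffected.

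The rule should still be corrected, because the endpoint will be reported with an interval and a p-value and a better derivation is already provided for.

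**What to change.** In SAP (Part 2) 5.2.2, derive oxygen-free days as 28 minus the last day on any oxygen support, in hospital or after discharge, using the collected start and end dates. Set the count to 0 for death by Day 28 and to 0 if the patient is still on oxygen at Day 28. Use WHO scores only as a cross-check for in-hospital days.

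The oxygen dates in protocol 6.2.2 are listed under the treatment period, so confirm that the end date is captured through Day 28, including after discharge. If it is not, ask for it at the existing Day 28 visit or call.

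The cost is a change of SAP wording and at most one extra data item, with no new procedure. The Part 2 SAP needs revision in any case, since its D-dimer strata (3 to under 5, and 5-fold ULN or more) predate Global Amendment 3.

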6.1 VISIT SCHEDULE

No study procedures may be initiated prior to the patient or patient's legally acceptable representative signing the informed consent. A patient who could not provide informed consent at the start of the trial due to the severity of the disease, may have their legally acceptable representative to sign the consent on their behalf, in accordance with applicable laws and regulations. Once patient is recovered, they would need to provide their own consent to continue in the study.

An independent witness may be required in the event that the patient is able to give verbal consent, but unable to sign the consent form. Please refer to [Section 8.1](#) for more details on consenting process.

During the Screening Visit at any time of the day or night, eligible patients who are exhibiting signs and symptoms of COVID-19 induced ARDS may be asked to participate in the study.

Patients fulfilling all eligibility criteria will be randomised to one of three treatment arms in Part 1, and to one of two treatment arms in Part 2.

For potential modification of trial conduct in case of restrictions due to COVID-19, please refer to [Appendix 10.4](#).

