7.5.2 Other Secondary endpoints

Other secondary endpoints are defined in [Section 5.2.2](#). In all cases, standard descriptive statistics will be presented, whether the endpoint is binary or continuous.

Binary safety endpoint

For the binary safety endpoint MBE up to day 6, analysed on the TS, there will be no adjustment for covariates. Therefore, the RD will be the difference between the two incidences and the p-value and 95% CI will be determined using the Chan and Zhang exact method.

For the NIV and IMV cohorts pooled, the RD 95% CI will be estimated between the two treatment arms using the same approach as for the key secondary efficacy endpoints. However, for this pooled investigation of MBE up to day 6, the baseline D-Dimer status (≥ 3 to <5 , ≥ 5 -fold ULN) and age covariates will not be included in the model. The p-value for homogeneity will be determined similarly.

Continuous efficacy endpoints

The three other secondary endpoints which are continuous in nature will be analysed using a restricted maximum likelihood (REML) based ANCOVA comparing the outcome, by treatment. The ANCOVA model will be adjusted for the default set of covariates as outlined in [Section 7](#) for the respective NIV and IMV patient cohorts. The treatment difference with 95% CI and p-values will be presented.

For the continuous efficacy endpoints, number of OFDs at day 28, and number of days in hospital, there are not expected to be any missing values by definition and as outlined in [Section 5.2.2](#).

[figure not shown]
For the continuous efficacy endpoint change from baseline in the $\text{PaO}_2/\text{FiO}_2$ at day 6, the baseline $\text{PaO}_2/\text{FiO}_2$ will also be included in the model as covariate for adjustment. For patients that have died, or who have been discharged from hospital, the handling rules are as outlined in [Section 5.2.2](#). Note, there are expected to be very few deaths or hospital discharges prior to day 6.

In addition, subgroup analyses of this $\text{PaO}_2/\text{FiO}_2$ endpoint will be conducted in the NIV patient cohort only and using the subgroups as outlined in [Section 6.4](#). An ANCOVA model will contain the baseline $\text{PaO}_2/\text{FiO}_2$, the subgroup of interest and the interaction between subgroup and treatment.

As sensitivity analyses, the unadjusted treatment effects will be estimated, using the same approach as the main analysis, but with only treatment in the model.

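### Oxygen-free days are set to missing for a patient who withdraws before Day 28 even after discharge off oxygen, at odds with two other SAP statements

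*SAP*

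**What the plan says.** Part 2 SAP 5.2.2 starts the OFD count when a patient reaches a lasting WHO score of 4 or less. It defines lasting as follows: "A lasting value of ≤ 4 means that the value cannot exceed 4 at a later timepoint". The formula is "If the patient is liberated from oxygen on Day x, then the number of OFDs is 28-x". Two special cases follow:

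- Withdrawal: "If a patient has withdrawn consent prior to day 28 then he will have a missing value for OFD".
- Death: "In any case, if the status of the patient at Day 28 is death, as determined from the vital status page then the OFD=0".

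The death rule overrides the others. No matching rule exists for a patient known to have been discharged.

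Two other places in the same SAP bear on this:

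- Section 6.6 says that after discharge the only further efficacy assessment is vital status at Days 28 and 90. It adds that the improvement which allowed a patient to be "discharged from hospital prior to day 28 will be taken into account in the determination of each of the endpoints".
- Section 7.5.2 says of OFD and length of stay that "there are not expected to be any missing values by definition and as outlined in" Section 5.2.2. The analysis is a REML-based ANCOVA, and the listed sensitivity analysis is the same model without covariates.

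**The concern.** Consider a patient who comes off oxygen, goes home and later withdraws consent. The in-hospital record gives the day of liberation, yet the patient drops out of the OFD analysis. A patient with an identical hospital record who does not withdraw contributes 28-x. A withdrawn patient known to be dead at Day 28 contributes 0. Among withdrawn patients with an informative record, the rule keeps the worst outcome and discards the favourable one.

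At stake is the complete-case difference in mean OFD. Each loss of this kind removes a high value and lowers that arm's mean. If the arms lose such patients at different rates, which is possible in an open-label trial, the difference moves up or down. Section 7.5.2 does not expect missing values, so it specifies no handling for them.

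**Working it through.** **No figure to reproduce.** The documents give no mean, standard deviation, power or withdrawal rate for OFD. The check is a comparison of texts, followed by an illustration of size.

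**Step 1: one patient across the endpoints.** Take an NIV patient who reaches a lasting WHO score of 4 on Day 10, is discharged and withdraws on Day 20.

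| Part 2 SAP endpoint | Result |
|---|---|
| Primary (Table 5.1: 1) | Event; later happenings are disregarded |
| Treatment failure, mortality (5.2.1) | Not failed, not dead, by last known status |
| Length of stay (5.2.2) | Value from the first discharge date |
| OFD (5.2.2), as written | Missing |
| OFD, same patient without withdrawal | 28 - 10 = 18 |

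Only OFD loses the patient. The score data behind the 18 and behind the missing value are the same. Footnote 11 of the protocol flow chart limits the WHO scale to the hospital stay, and SAP 6.6 confirms that only vital status follows discharge.

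**Step 2: illustration of size.** Inputs:

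- Recovered share r: 0.30 on SOC and 0.50 on alteplase. These are the event rates for improvement or discharge in protocol 7.5, used as a stand-in for the share with OFD above 0. For a patient starting at WHO 6, a two-point improvement is a score of 4, so the stand-in is reasonable but not exact.
- OFD per recovered patient m: 14 days (assumption; range 10 to 18), and 0 for all others.
- Share w of recovered patients who withdraw after discharge off oxygen: 0 to 20% (assumption).

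Arm mean with all patients: r × m, which gives 0.50 × 14 = 7.00 and 0.30 × 14 = 4.20. The difference is 2.80 days.

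Arm mean after the rule: m × r(1 - w) / (1 - rw).

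- Alteplase, w = 10%: 14 × 0.45/0.95 = 6.63.
- SOC, w = 10%: 14 × 0.27/0.97 = 3.90.
- Alteplase, w = 20%: 14 × 0.40/0.90 = 6.22.
- SOC, w = 20%: 14 × 0.24/0.94 = 3.57.

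| Withdrawal among recovered patients | Difference (days) | Change |
|---|---|---|
| None | 2.80 | – |
| 10% in both arms | 6.63 - 3.90 = 2.74 (unrounded means) | -2% |
| 20% in both arms | 6.22 - 3.57 = 2.65 | -5% |
| 10% in SOC only | 7.00 - 3.90 = 3.10 | +11% |
| 10% in alteplase only | 6.63 - 4.20 = 2.43 | -13% |

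The shifts scale with m. For m = 10 to 18, the SOC-only shift is +0.22 to +0.39 days and the alteplase-only shift is -0.26 to -0.47 days.

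**Step 3: set against the noise.** With about 140 alteplase and 70 SOC patients in the NIV cohort (protocol 7.5), the same model gives a standard error of 14 × √(0.25/140 + 0.21/70) = 0.97 days. The largest shift at m = 14 is 0.37 days, or 0.37/0.97 = 0.38 standard errors. In patient numbers, 10% of recovered patients is about 2 of 21 on SOC or 7 of 70 on alteplase.

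**The case against.** The strongest defence is that OFD requires a score which stays at 4 or less up to Day 28, and that this cannot be verified after withdrawal. The protocol offers some support: section 6 invites discharged patients to later visits, the flow chart marks the WHO scale at Day 28, and section 5.1.2 has oxygen-free days captured from source documents to Day 28. On that view, missing is the honest value for someone who can no longer be followed, and the Part 1 SAP treats ventilator-free days in the same way.

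This does not rescue the rule. The SAP derives OFD from the WHO scale, the flow-chart footnote limits that scale to the hospital stay, and SAP 6.6 says no efficacy data other than vital status follow discharge. Persistence is therefore assumed for every discharged patient. The defence does hold for a patient who withdraws while still in hospital: a single score of 4 or less is not a lasting one and should not earn 28-x in the main analysis. It also holds for a patient discharged or transferred while still on oxygen.

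Some stronger readings are not supported:

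- A reader might infer that everyone who withdraws is lost. Known deaths are not.
- A reader might take 7.5.2 as a flat claim that nothing is missing. It says missing values are not expected, and withdrawal is called unlikely. The conflict is that the definition it points to itself creates them.
- A reader might infer that withdrawal is tied to recovery by design, because protocol 6.1 says of patients enrolled through a representative: "Once patient is recovered, they would need to provide their own consent to continue in the study". This is a possible route only. Recovery there may mean regained capacity to consent, perhaps while still on oxygen. No share of such patients is given, and the documents do not say that declining is recorded as withdrawal.
- A reader might conclude that the OFD estimate is biased. The documents show only that it could be.

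**Conclusion.** The inconsistency is real and the point is minor. SAP 5.2.2 drops patients known to have gone home off oxygen, conflicts with 6.6 and 7.5.2, and treats them differently from otherwise identical patients who do not withdraw. The effect on the OFD difference can go either way. Its size is unknown, since it depends on a withdrawal rate that the documents do not give. With 30% and 50% recovered, 14 days each, and either equal withdrawal of up to 20% of recovered patients or 10% in one arm only, a difference of 2.8 days becomes about 2.4 to 3.1. The ends of that range need all such withdrawal to fall in one arm. OFD is analysed in a non-confirmatory manner (protocol 7.2.3) and lies outside the testing hierarchy, so no confirmatory conclusion is affected.

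**What to change.** Before the Day 28 snapshot:

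1. In SAP 5.2.2, assign OFD = 28-x to a patient who withdraws after hospital discharge with a last recorded WHO score of 4 or less, where x is the day that run began. Keep the override for death.
2. Keep OFD missing for patients who withdraw while still in hospital, or who were discharged or transferred while still on oxygen.
3. Add a sensitivity analysis for those left missing: OFD = 0 if last seen on oxygen, and 28-x for inpatients last recorded at 4 or less.
4. Reword 7.5.2 to say that few missing values are expected and that they arise from withdrawal before discharge off oxygen.

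The cost is a few SAP sentences, a small derivation change and one extra analysis, all from data recorded before withdrawal. The downside is that the new value assumes the oxygen-free state lasts after discharge, as the SAP already assumes for other discharged patients.
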